3.3 SAMPLE SIZE

The sample size calculation was based on two co-primary outcomes:

1. 28-day mortality, for which we want to show non-inferiority of the PCT-guided assessment as compared to current standard practice, using an absolute 2.5% non-inferiority margin. Assuming 28-day mortality of 15% in patients managed as suspected sepsis treated in the ED, any increase in 28-day mortality from 15% to not more than 17.5% would be considered non-inferior. For 90% power and one-sided 5% significance level, the sample size required is 7002, assuming there is no difference in 28-day mortality between arms. Our patient focus group were also consulted on the 2.5% non-inferiority margin and felt that this was acceptable if there were mechanisms to monitor trial outcomes, and if this was what was needed to provide a sample size which would ensure the trial could be completed as well as answer the research question.

2. Initiation of antibiotic treatment, for which we want to show superiority. Currently, around 90% of patients managed as suspected sepsis receive antibiotics (Royal Liverpool and Broadgreen University Hospitals NHS Trust, unpublished data). Reducing this by 10 percentage points to 80% would be seen as a success. To detect such an effect with 90% power and a two-sided 5% significance level, the sample size required is 532, which is substantially lower than what is needed for the non-inferiority endpoint. With 7002 patients, we would be able to detect effects as small as a reduction from 90% to 87.6% prescriptions with 90% power.

Accounting for 5% dropout, a fixed-sample design would need a total sample size of 7372.

We planned to conduct one interim analysis (after 50% of patients provided data) with options to stop the trial early using group-sequential boundaries based on O'Brien-Fleming type alpha spending (O'Brien & Fleming, 1979, DeMets & Lan, 1994). We used a hierarchical approach (Figure 2) to recommend stopping for effectiveness if:

TPL/008/2(v1.0)

Canolfan Ymchwil Treialon

Short title:	ISAP / SAP Template
--------------	---------------------

- the PCT-guided assessment was non-inferior in terms of 28-day mortality and superior in terms of initiation of antibiotics, or
- the PCT-guided assessment was superior in terms of 28-day mortality (i.e., a significant reduction to less than 15%).

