4. STATISTICAL PRINCIPLES

4.1 LEVELS OF CONFIDENCE AND P-VALUES

ISAP / SAP Template

Short title:

The trial follows the group-sequential approach with one interim analysis; thus, p-values will be adjusted using the O'Brien-Fleming type alpha spending approach. For the hypothesis testing, any p-value less than the adjusted level of significance at the final analysis (Table 1 in Section 3.5.2) will be considered sufficient evidence to reject the hypothesis.

We will consider the 95% confidence limit (corresponding to a 5% significance level) as a benchmark for all analyses. We will estimate a two-sided 90% confidence interval (corresponding to a 95% one-sided confidence level) to assess the non-inferiority of the 28-day mortality outcome, and a two-sided 95% confidence interval to assess the superiority of the IV antibiotic initiation outcome. We will report both unadjusted and OBF adjusted confidence intervals for both co-primary outcomes.

We will also report bias-adjusted confidence intervals for group sequential designs, calculated using Jennison and Turnbull's repeated CI approach (Jennison & Turnbull, 1989).

Results will be presented in line with the CONSORT statement and its extensions for non-inferiority (Piaggio et al., 2012) and adaptive designs (Dimairo et al., 2020).

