6.2.1.2 PRIMARY OUTCOME ANALYSIS

We will use complete case analysis for the co-primary outcomes, meaning that we will only include participants with valid responses to both co-primary outcomes in the primary analysis. We will fit separate two-level logistic regression models (patients nested within sites) to model both co-primary outcomes, controlling for baseline NEWS2 score (minimisation variable). Results will be reported as risk differences with corresponding confidence intervals (calculated via the delta method (Norton et al., 2013)); a two-sided 90% interval for 28-day mortality (OBF adjusted to 90.18%), and a two-sided

TPL/008/2(v1.0)

Canolfan Ymchwil Treialon

Short title: ISAP / SAP Template	
----------------------------------	--

95% interval for IV antibiotic initiation at 3 hours (OBF adjusted to 95.04%). Non-inferiority in 28-day mortality will be concluded if the upper bound of the confidence interval is below +2.5% on the risk difference scale.

The individual analyses for the co-primary outcomes and corresponding inferences are described in the table below:

128-day mortality228-day mortality	Non-inferiority test with a margin of 2.5% H ₀ : $p_2 - p_1 \ge 0.025$ Superiority test	O'Brien-Fleming alpha spending (one-sided alpha = 0.05) Reject null if P < 0.0491 Critical value = 1.654 O'Brien-Fleming alpha spending (one-sided alpha = 0.05)
= = = = = = = = = = = = = = = = = = = =	Superiority test	O'Brien-Eleming alpha spending (one-sided alpha = 0.05)
	$H_0: p_1 - p_2 \le 0$	Reject null if P < 0.0491 Critical value = 1.654
3 IV antibiotic initiation at 3 hour	H ₀ : $p_1 - p_2 \neq 0$	O'Brien-Fleming alpha spending (two-sided alpha = 0.05) Reject null if P < 0.0496 Critical value = 1.964 the control and intervention arm, respectively.

 Table 5: Inferences for analyses of co-primary outcomes

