6.2.6 SUBGROUP ANALYSES

We will conduct seven separate subgroup analyses, stratified by:

- The organ system of the infection (initial working diagnosis):
 - Upper respiratory tract infection
 - Skin/soft tissue infection
 - Urinary tract infection/urosepsis
 - Central nervous system infection
 - Gastrointestinal tract/abdominal infection
 - Bone/joint/muscle infection
 - Lower respiratory tract infection/community-acquired pneumonia
 - Sepsis (unknown source)
 - Other infections
 - Not infection
- Risk category based on NEWS2 score at baseline:
 - ≤4
 - 5-6
 - ≥7
- Managed as suspected COVID-19 during admission:
 - Yes
 - No
- Positive COVID-19 test result +/- 5 days from admission:
 - Yes
 - No
- PCT machine used at time of recruitment:
 - BRAHMS PCT-direct

TPL/008/2(v1.0)

Canolfan Ymchwil Treialon

Short title: ISAP / SAP Template

- PathFast BRAHMS PCT
- Recruitment date:
 - Before 1st December 2021
 - Between 1st December 2021 and 30th November 2022
 - After 30th November 2022
- Level of site ED crowding (percentage of patients who spent >12 hours from decision to admit to admission) at time of randomisation:
 - Upper tercile of national monthly figures
 - Middle tercile of national monthly figures
 - Bottom tercile of national monthly figures

We will investigate whether the treatment effect varies between subgroups by including the subgroup variable as a covariate in the main analysis model, both with and without a treatment-arm interaction term. The models with and without the interaction term will be compared using a likelihood-ratio test (LRT). We will report the LRT χ^2 statistic and illustrate the direction of the subgroup effect using forest or interaction plots.

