We will also assess whether adherence to the intervention varies according to levels of ED crowding at the time of randomisation. We will conduct a two-level logistic regression (patients nested within sites) with algorithm adherence (yes/no) as the outcome variable and the level of ED crowding as the explanatory variable, controlling for baseline NEWS2 score (minimisation variable). NHS England publishes monthly A&E attendances and emergency admissions data. We will calculate the percentage of emergency admission patients who spent >12 hours from decision to admit to admission per month per site and compare these to the national monthly figures. We will rerun the co-primary analyses for subgroups of the least, middle, and most crowded EDs. As an exploratory analysis we may include ED crowding as an additional covariate and include time varying interaction terms. If the data allows, we may also explore the effect of daily ED crowding levels on the co-primary outcomes for a subgroup of sites.

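### The interaction tests for ED crowding, and for PCT machine if it is fixed by site, make no allowance for site-to-site variation in the PCT effect

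*SAP*

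**What the plan says.** Section 6.2.1.2 of the SAP defines the main model: "We will fit separate two-level logistic regression models (patients nested within sites) to model both co-primary outcomes", adjusted for baseline NEWS2. Section 6.2.6 investigates effect modification "by including the subgroup variable as a covariate in the main analysis model, both with and without a treatment-arm interaction term", and then: "The models with and without the interaction term will be compared using a likelihood-ratio test (LRT"). No random arm effect by site, site-clustered variance or comparable device is named. The words random intercept do not appear either, but that is the usual meaning of a two-level model with no further specification.

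Two of the seven subgroup variables are not patient characteristics. For crowding, section 6.2.6 states: "We will calculate the percentage of emergency admission patients who spent >12 hours from decision to admit to admission per month per site", to be compared with national monthly figures. The other is listed as "PCT machine used at time of recruitment", and nothing says whether a site kept one machine throughout. The deviation log records that the crowding analysis used the site's percentage instead of the tercile.

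Section 4.1 sets the yardstick: "We will consider the 95% confidence limit (corresponding to a 5% significance level) as a benchmark for all analyses". The dummy Table A4 has a p-value column for each interaction. The SAP gives neither the number of sites nor any figure for how far the PCT effect may differ between them.

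**The concern.** Each fit in the comparison has one arm effect common to all sites, apart from the interaction itself. Every patient therefore counts as independent information on how the effect differs between machines or crowding levels. For a modifier shared by everyone at a site, the independent units are the sites. If the PCT effect differs between departments for unrelated reasons, sites with larger effects will by chance fall more in one modifier group than another. The likelihood-ratio test then credits that imbalance to the modifier.

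Some variation is plausible on the plan's own terms. The trial is open-label, section 4.2.1 lets clinicians overrule the algorithm, and section 6.2.6 itself asks whether adherence changes with crowding. None of this shows how large the variation is.

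At stake are service-level statements, for example that PCT guidance works with one analyser or only in less crowded departments. These could rest on p-values that overstate the evidence.

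**Working it through.** **Scale.** "For 90% power and one-sided 5% significance level, the sample size required is 7002" (section 3.3). Check: per arm (1.645 + 1.282)² × 2 × 0.15 × 0.85 / 0.025² ≈ 3,495, so 6,990 in total against 7002. The antibiotic calculation (90% v 80%) reproduces exactly at 532. N = 7002 is used below.

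**Inputs from the SAP.** 1:1 allocation, mortality 15% in both arms, IV antibiotics 90% v 80%, test level 5%.

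**Assumptions not in the SAP.** 10, 20 or 40 sites, and a between-site SD of the PCT log odds ratio (tau) from 0 to 0.3. For scale, the planned fall from 90% to 80% is a log odds ratio of ln(0.8/0.2) − ln(0.9/0.1) = −0.81, so tau = 0.2 is about a quarter of it. The simulations also assume a site-intercept SD of 0.3 and 24 months.

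**Closed form: two-group modifier wholly fixed by site, equal site sizes.** One site's log odds ratio has sampling variance v = (2/n_site) × [1/(p₀(1−p₀)) + 1/(p₁(1−p₁))]. The planned test uses v as its error, but the true variance is v + tau². The rejection rate with no true interaction is 2 × (1 − Φ(1.96/√(1 + tau²/v))).

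With 20 sites, n_site = 350.1. For mortality, v = (2/350.1) × (7.843 + 7.843) = 0.0896. At tau = 0.2, √(1 + 0.04/0.0896) = 1.203 and 1.96/1.203 = 1.63, which gives 10.3%.

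| Outcome | Sites | v | tau 0 | 0.1 | 0.2 | 0.3 |
|---|---|---|---|---|---|---|
| Mortality | 10 | 0.0448 | 5.0% | 7.6% | 15.4% | 25.8% |
| Mortality | 20 | 0.0896 | 5.0% | 6.3% | 10.3% | 16.6% |
| Mortality | 40 | 0.1792 | 5.0% | 5.6% | 7.6% | 11.0% |
| IV | 10 | 0.0496 | 5.0% | 7.4% | 14.5% | 24.3% |
| IV | 20 | 0.0992 | 5.0% | 6.2% | 9.8% | 15.6% |
| IV | 40 | 0.1984 | 5.0% | 5.6% | 7.4% | 10.4% |

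**Simulation: mortality, 20 sites of unequal size, site intercepts fitted as fixed effects, 1,000 runs per cell** (Monte Carlo SE about 1 point).

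| Modifier | tau 0 | 0.1 | 0.2 | 0.3 |
|---|---|---|---|---|
| Machine fixed by site | 5.5% | 6.5% | 12.5% | 20.4% |
| Every site changes machine partway | 5.2% | 4.9% | 6.1% | 6.0% |
| Crowding terciles, 100% of variance between sites | 5.4% | 6.8% | 15.6% | 28.4% |
| 70% between sites | 4.3% | 6.0% | 8.3% | 13.6% |
| 30% between sites | 5.2% | 6.7% | 6.1% | 8.0% |
| 0% between sites | 5.4% | 4.4% | 5.9% | 5.3% |

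The IV outcome at planning rates behaves similarly. With 20 sites and 70% between sites it gives 7.0% and 13.0% at tau 0.2 and 0.3.

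**Effect of the remedy: mortality, 20 sites, site-fixed modifier, maximum likelihood, 400 runs per tau** (SE 1 to 2 points). With a site random intercept only, rejection is 5.8%, 11.5% and 17.0% at tau 0, 0.2 and 0.3. With a site-level random arm effect added to both fits it is 4.3%, 6.0% and 6.0%.

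**The case against.** The case against has four parts.

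- **The excess is conditional.** At tau = 0 the planned test holds its level, at 4% to 6% in every scenario. At tau = 0.1, or with 40 sites, the excess is modest. The SAP gives no estimate of tau. This stands: a reader might infer that the planned p-values are simply too small, and the document does not support that.
- **Machine is not shown to belong to the site.** The listing refers to the time of recruitment, which leaves room for a change within a site. If all sites changed partway, the excess almost disappears. This also stands, so the point about machine holds only if machine was mainly fixed by site.
- **Crowding moves from month to month.** Only its between-site share causes trouble, so treating it as wholly site-fixed overstates the problem. The deviation log gives rising crowding as the reason for dropping terciles, so the tercile rows above illustrate the planned analysis and not the one reported. But "per month per site and compare these to the national monthly figures" still describes a quantity measured on the site, and nothing suggests that its between-site share is nil.
- **The consequence is limited.** The effectiveness decision in Table 3 does not use these tests, and no rule turns an interaction p-value into a claim. This is correct and sets the priority.

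A random arm effect by site also leaves any site-by-month variation in the effect unmodelled. The remedy is therefore an improvement and not a complete answer.

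**Conclusion.** The point holds in conditional form. The plan's interaction test assumes, without saying so, that the PCT effect does not vary between sites apart from the modifier. For crowding, and for machine if it is mainly fixed by site, a departure from that assumption raises the false-positive rate. With 20 assumed sites and tau of 0.2 to 0.3, the rate is about 10% to 17% for a modifier wholly fixed by site. For crowding terciles with 70% of their variance between sites it is about 8% to 14%, and with 30% about 6% to 8%. Fewer sites make it worse and more sites make it better. These figures depend on a site number and a tau that the SAP does not supply.

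It would go too far to infer from this that either reported interaction is spurious, or that the co-primary results are in doubt. The co-primary tests do not use these interactions, and the other five subgroup variables are not part of this point. The priority is minor.

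**What to change.** In section 6.2.6 and Table 6, for ED crowding (as terciles, or as the site percentage used according to the deviation log), add a site-level random arm effect to both models being compared. Do the same for PCT machine if site records show that it was mainly fixed by site. The SAP should state which applies. If the model does not converge, use a random-effects meta-regression of site-specific effects on the modifier. Report the result beside the planned likelihood-ratio test, on both co-primary outcomes. Because the deviation log shows that analysis has already taken place, log this as an addition. If the change is not made, state that site variation in the PCT effect is assumed to be nil.

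The cost is one variance term in up to four tests (two modifiers by two outcomes). If the effect does not in fact vary by site, the test may be slightly conservative with a small loss of power (4.3% rejection at tau = 0 in the check above, within simulation error of 5%). Convergence may also be difficult.

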6.3 MISSING DATA

During data entry, validations have been written into the system to minimise the amount of missing data, however, missing data may still occur. The frequency and percentage of missing values will be reported overall and by arm. If missing primary outcome data is greater than 5% (as accounted for in the sample size calculation), we will conduct sensitivity analyses using multiple imputations (separately for both randomisation groups) (Sullivan et al., 2018). Missing data will be investigated for cause and extent and multiple imputation. The assumption of missingness at random (MAR) will be tested by analysing each baseline covariate in a separate logistic regression model to determine which (if any) are associated with the missingness of the primary outcome, and the associated p-values will be reported alongside the summary statistics. Missing observations will be replaced by multiple imputations by chained equations (MICE). A sensitivity analysis will be conducted on the primary analysis, including any baseline factors that were found to be associated with the

TPL/008/2(v1.0)

Canolfan Ymchwil Treialon

Short title:	ISAP / SAP Template

missingness of the primary outcome. Any changes to the assumptions made in the primary analysis will be considered in a sensitivity analysis.

6.4 ADDITIONAL ANALYSES

We will compare the initial working diagnosis versus the final diagnosis by arm.

We may perform a linear regression analysis on an intention to treat basis using the primary analysis population as defined in section 4.3, utilising two-level models to allow for patients nested within sites, to explore the differences in Daily Defined Doses of antibiotics by arm.

The health economics and qualitative analysis plans are detailed separately from the SAP.

6.5 HARMS

The trial population comprises very sick adults, and hospitalisation is normal in this population. Events such as prolongation of existing hospitalisation, life threatening events and death are also expected in this population and are recorded as part of outcome data collection and therefore are not subject to expedited reporting on an SAE form.

For the purposes of this trial the following events will not require reporting as SAEs:

- Death
- Life threatening event
- Hospitalisation or prolongation of hospitalisation
- Admission to ICU
- Non-serious AEs potentially attributable to PCT test and step-down approach will be collected as part of routine follow-up at 28 days.
- Other non-serious AEs will not be collected.

These events will be recorded in the participant's notes and on the relevant CRFs.

The following will be reported as SAEs within 24 hours:

- Events resulting in persistent or significant disability or incapacity
- Congenital anomalies or birth defects

The frequency (percentage) of AEs and SAEs will be tabulated overall and by trial arm and compared using a chi-square test.

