3. STUDY MATERIALS

3.1 TRIAL DESIGN

Parallel, two-arm, open-label, individually randomised controlled trial with two co-primary endpoints, an internal pilot phase, and group-sequential stopping rules for effectiveness. Participants are randomised in a ratio of 1:1 to PCT-guided assessment added to NEWS2 and local standard care, or NEWS2 and local standard care alone. The participant flow diagram (Figure 1) provides further details.

Canolfan Ymchwil Treialon

[figure not shown]

Figure 1: PRONTO trial participant flow diagram.

TPL/008/2(v1.0)

Short title:

ISAP / SAP Template

Canolfan Ymchwil Treialon

Short title: ISAP / SAP Template

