3.2 RANDOMISATION

Individual patients with suspected sepsis were randomised in a 1:1 ratio to either standard clinical management based on NEWS2 (control), or standard clinical management based on NEWS2 plus PCT-guided assessment (intervention). We used minimisation with NEWS2 score and site as stratification factors and added a random element to reduce the risk of subversion. This was implemented in a secure 24-hour web-based randomisation programme controlled centrally by the Centre for Trials Research.

The first patient was allocated at random. For each subsequent patient the software calculated the covariate sums as explained in Altman & Bland (2005) and determined which arm the patient should be allocated to in order to minimise the covariate imbalance. The patient was then randomised with an 80% chance of being allocated to the arm that minimised the imbalance (and a 20% chance of being allocated to the other arm). If neither arm minimised the imbalance because the covariate sums were equal for both arms (i.e., a state of perfect balance) the patient was allocated at random.

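### Section 6.5 keeps non-serious AEs only if attributed to the intervention, then tests AE frequency between arms, so that test leans towards an excess in the PCT arm

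*SAP*

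**What the plan says.** Three statements in SAP section 6.5 bear on the point.

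- What is collected: "Non-serious AEs potentially attributable to PCT test and step-down approach will be collected as part of routine follow-up at 28 days".
- What is not: "Other non-serious AEs will not be collected".
- What is done with the data: "The frequency (percentage) of AEs and SAEs will be tabulated overall and by trial arm and compared using a chi-square test".

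The SAEs named in the same section, such as "Events resulting in persistent or significant disability or incapacity", carry no attribution condition.

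Section 3.1 describes a "Parallel, two-arm, open-label, individually randomised controlled trial", with participants allocated to PCT-guided assessment added to NEWS2 and local care, "or NEWS2 and local standard care alone".

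Section 3.7 gives a different picture of AE collection. It has nurses log outcome data every day for everyone recruited, and its Table 2 includes an adverse-events row taken from charts and notes, with no attribution condition.

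Adverse antibiotic outcomes are handled separately as secondary outcome 9 (sections 6.1.3 and 6.1.5, and Table 7 in 6.2.1.3). They are compared by arm with logistic regression, again without an attribution condition.

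**The concern.** A between-arm test of event frequency is informative only if an event of a given kind has the same chance of being recorded in either arm. Section 6.5 makes recording depend on whether someone links the event to the intervention. A control participant has no trial PCT test to which an event could be linked, and whoever judges the link knows the allocation. The same clinical event could therefore be counted in a PCT participant and dropped in a control under the second statement. The chi-square then partly tests the collection rule.

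The result would appear in the report beside the 28-day mortality non-inferiority result, which is the trial's main safety question. A significant excess could be an artefact, and a non-significant result would say little about relative safety. The pooled percentage has the same weakness, because it mixes two arms with different chances of contributing events.

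**Working it through.** **Inputs from the SAP.** Section 3.2: "Individual patients with suspected sepsis were randomised in a 1:1 ratio". Section 3.3: "For 90% power and one-sided 5% significance level, the sample size required is 7002, assuming there is no difference in 28-day mortality between arms". Section 3.3 also gives a maximum of 7676. The harms section states no figure of its own. The SAP gives no AE rate and no expected capture in controls; the values used below are assumptions.

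**Reproducing the denominator.** With 15% mortality in both arms, a margin of 0.025, one-sided 5% and 90% power:

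n per arm = 2 × 0.15 × 0.85 × (1.645 + 1.282)² / 0.025² ≈ 3,495, or 6,990 in total.

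The SAP states 7002, which is close enough to accept. Half of 7002 is 3,501 per arm; half of 7676 is 3,838.

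**How few events give a small p-value.** For x events among n in the PCT arm and none among n in controls:

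- Uncorrected: χ² = 2n·x / (2n − x)
- Continuity-corrected: χ² = 2n·(x − 1)² / [x(2n − x)]

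With n = 3,501:

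- x = 3, uncorrected: 7002 × 3 / 6999 = 3.00, p = 0.083
- x = 4, uncorrected: 7002 × 4 / 6998 = 4.00, p = 0.045
- x = 5, corrected: 7002 × 16 / (5 × 6997) = 3.20, p = 0.074; Fisher p = 0.062
- x = 6, corrected: 7002 × 25 / (6 × 6996) = 4.17, p = 0.041; Fisher p = 0.031

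So 4 events suffice uncorrected, and 6 with the corrected or Fisher test. The thresholds are the same at 3,838 per arm. With 4 against 0 the expected count is 2 per arm, where the uncorrected test is least reliable, so both versions are given.

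**When the true rates are equal.** Let the true AE rate be the same in both arms, with all events recorded in the PCT arm and only a share recorded in controls. Exact binomial enumeration with n = 3,501 and the uncorrected test at two-sided 5% gives the probability of a significant excess in the PCT arm:

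| True rate (assumed) | No control capture | 10% captured | 50% captured | 100% captured |
|---|---|---|---|---|
| 0.03% | 2% | 2% | 1% | 1% |
| 0.05% | 10% | 9% | 4% | 2% |
| 0.1% | 46% | 34% | 10% | 2% |
| 0.2% | 92% | 68% | 17% | 2% |
| 0.5% | about 100% | 98% | 41% | 2.5% |
| 1% | about 100% | about 100% | 69% | 2.5% |

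A check on one cell: at 0.1% the expected count is 3,501 × 0.001 = 3.5, and the chance of 4 or more is 46%.

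The last column is what equal recording would give. The bias does not need a zero control count: at a true rate of 0.5%, recording half of the control events raises the chance of a false excess from 2.5% to 41%. At very low event rates the test seldom rejects, whatever the capture.

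**The case against.** Several points can fairly be made for the plan.

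*A zero control count is not stated.* A reader might infer that controls are at zero by construction. The SAP does not say so. No text limits collection to the PCT arm, the 28-day follow-up applies to both arms, and step-down approach is not defined, so some control events might qualify. This stands. The inference is firm for events due to the PCT test itself and weaker for the rest. It bears on how strong the bias is; its direction is unchanged, because lower capture in controls is enough.

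*The test need not show harm.* A reader might infer that the analysis will show harm from PCT whatever the truth. It will not: with fewer than 4 recorded events against none, even the uncorrected test is not significant. This stands too.

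*Other harms are compared properly.* SAEs and secondary outcome 9 have no attribution filter. Mortality, critical care admission and readmission are analysed by arm, and effectiveness is decided on the co-primary outcomes (Table 3 in section 6.1.1). All this stands and limits the consequences. The questioned p-value feeds no decision rule.

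*The tested AEs may be a wider set.* They might be those in Table 2, or include the deaths, admissions and other events listed in section 6.5 as exempt from SAE reporting. This does not rescue the plan. Section 6.5 says outright that other non-serious AEs are not collected, so the two sections disagree on which data feed the test, and the SAP does not settle it.

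**Conclusion.** The point holds for the chi-square comparison of non-serious AEs. Collection tied to the intervention, in an open-label trial whose controls do not have it, makes lower capture in controls likely. The comparison is then biased towards an excess in the PCT arm and should not be read as evidence on relative safety.

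The size of the bias depends on two quantities that the SAP does not give: the AE rate and the share recorded in controls. Over the assumed values above, the chance of a false PCT excess runs from about 1% or 2%, when events are very rare, to about 100% when they are commoner and poorly captured in controls. Equal recording would give at most about 2.5%.

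The bias does not extend to SAEs, to secondary outcome 9 or to the co-primary outcomes. The contradiction between section 6.5 and Table 2 stands without any of these assumptions.

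**What to change.** Amend the analysis statement in section 6.5:

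1. Report intervention-attributed non-serious AEs descriptively, by arm if any were recorded in controls, with no between-arm test and no pooled percentage. State that capture may differ between arms.
2. Base between-arm safety comparisons on events ascertained alike in both arms: mortality, critical care admission, readmission, adverse antibiotic outcomes and SAEs. Apart from SAEs, these already have planned by-arm models.
3. Reconcile section 6.5 with the adverse-events row of Table 2, saying which AEs were recorded, in whom and when, and define step-down approach or point to its definition.

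The cost is wording and one p-value. Control-arm events, if any were recorded, stay in the table. Section 3.6 puts the end of data collection in November 2023 and the deviation log shows analyses during 2024, so collection can no longer be changed. The change belongs in the deviation log and the final report.
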